8.2.2 Adverse Events

8.2.2.1 Collection of Adverse Events

It is the responsibility of the investigator to collect all AEs (both serious and non-serious) derived by spontaneous, unsolicited reports of patients, by observation and by interval open questioning.

8.2.2.2 Definitions

An AE is any untoward medical occurrence that occurs in a patient or clinical investigation subject administered a pharmaceutical product, and which does not necessarily have to have a causal relationship with this treatment. An AE can therefore be any unfavorable and unintended sign (including a clinical significant abnormal laboratory finding), symptom, or disease temporally associated with the use of an investigational product, whether or not considered related to the product.

All AEs, including intercurrent illnesses, occurring during the study will be documented in the CRF. Underlying disease worsening (MS), hospitalization for routine study activities, and abnormal laboratory results associated with MS, will not be considered as AEs. Relapse of underlying malignancy will not be considered as an AE/SAE but will be captured and analyzed separately. MS will not be considered as an AE, unless it meets any of the seriousness criteria, in

particular hospitalization or death. Concomitant illnesses, which existed prior to entry into the study, will not be considered AEs unless they worsen during the treatment period. Pre-existing conditions will be recorded in the CRF on the Medical History or appropriate page. AEs will be captured after informed consent signed until 30 days post the completion of the last intervention. (Week 52).

8.2.2.3 Assessment of Adverse Events

Each AE will be assessed by the investigator with regard to the following categories.

8.2.2.3.1 Seriousness

A serious AE (SAE) is defined as any untoward medical occurrence that at any dose:

- Results in death;
- Is life-threatening;
this means that the patient is at risk of death at the time of the event; it does not mean that the event hypothetically might have caused death if it were more severe.
- Requires inpatient hospitalization or prolongation of existing hospitalization;
- Results in persistent or significant disability or incapacity;
- Is a congenital anomaly or birth defect;
- Is an important medical event(s) that may not be immediately life-threatening or result in death or hospitalization but that may jeopardize the patient or require intervention to prevent one of the above outcomes. Examples of such events are intensive treatment in an emergency room or at home for allergic bronchospasm; blood dyscrasias or convulsions that do not result in hospitalization; or development of drug dependency or drug abuse.

Medical and scientific judgment should be exercised in deciding whether a case is serious.

8.2.2.3.2 Intensity

The intensity of each AE must be assessed by the investigator using one of the following categories, and recorded in the CRF:

- Mild: An AE that does not interfere with usual activities;
- Moderate: An AE that interferes with usual activities;
- Severe: An AE that prevents usual activities.

8.2.2.3.3 Causality

The investigator will assess the causality / relationship between the study treatment groups (corticosteroids or ECP) and the AE and record that assessment in the CRF.

The most likely cause of an SAE (e.g., disease under treatment, concomitant disease, concomitant medication, other) will be indicated on the CRF with details of the concomitant disease or medication or other cause.

The causal relationship of the AE to study drug/device will be described in terms of:

- Probable: the AE:
 - Follows a reasonable temporal sequence from administration of the study drug/device.
 - Could not be reasonably explained by the patient's clinical state, environmental or toxic factors or other therapies administered to the subject.
 - Disappears or decreases on cessation or reduction in dose of the study drug/device.

- Follows a known pattern of response to the study drug/device.
- Reappears or worsens upon rechallenge.
- Possible: the AE:
 - Follows a reasonable temporal sequence from administration of the study drug/device.
 - Could be reasonably explained by the patient’s clinical state, environmental or toxic factors or other therapies administered to the subject.
 - Follows a known pattern of response to the study drug/device.
- Unlikely: the AE
 - Does not follow a reasonable temporal sequence from administration of the study drug/device.
 - Could be reasonably explained by the patient’s clinical state, environmental or toxic factors or other therapies administered to the subject.
 - Does not follow a known pattern of response to the study drug/device.
 - Does not reappear or worsen upon rechallenge.
- Not related:
 - The AE does not meet the above criteria.
 - There is sufficient information that the etiology of the AE is not related to the study drug/device.

For SAEs related or possibly related to ECP, the investigators will also provide an assessment of whether the SAE is related to the drug, UVADEX[®] (methoxsalen) Sterile Solution or the procedure/device.

8.2.2.4 Recording Adverse Events

Adverse event reporting will extend from signing of informed consent until completion of study (Week 52) or 30 days after the last study intervention. Adverse events occurring after the end of the study should be reported to the Sponsor by the investigator if the investigator considers there is a causal relationship with the study treatment.

All AEs (including AEs resulting from active standard of care medication and study instrument), regardless of the relationship to study drug, will be recorded in the CRF.

In addition, the technician performing the ECP procedure will observe and record any AEs that occur during the procedure. Treatment will be stopped if the patient cannot tolerate the procedure.

All AE reports should contain a brief description of the event, date of onset, date of resolution, intensity, treatment required, relationship to study drug, action taken with the study drug, outcome, and whether the event is classified as serious.

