3. OVERALL DESIGN AND PLAN OF THE STUDY

3.1 Overview

This is a Phase II randomized, open-label study to evaluate the efficacy of extracorporeal photopheresis (ECP) versus IVMP on disability progression in subjects with SPMS. At the initial screening visit, an extensive medical history will be obtained and a detailed neurological examination will be performed to determine eligibility. Subjects who meet eligibility criteria will be enrolled in one of two study arms. Subjects will be randomized at a 1:1 ratio to receive ECP (study arm) or active treatment with intravenous methylprednisolone pulses (control arm) administered every 4 Weeks (1 gram per infusion) for 52 weeks.

ECP will be administered according to the following schedule:

Study Arm: Weeks 1-8: 3 times per week

Weeks 9-16: Twice per week

Weeks 17-36: Treatment on two consecutive days every 2 weeks (or optionally, one treatment per week)

Weeks 37-43: Once every 2 weeks

Weeks 44-52: Once every 4 Weeks

[figure not shown]
All subjects, including patients who receive corticosteroids, will be evaluated using the MSFC tool at baseline and every 3 months through 2 years (See Section 9.1 for timing of the schedule of assessments). They will also be scored using the EDSS at baseline and every 3 months through 2 years. Subjects in the control arm will be evaluated by MSFC and EDSS during the week prior to their next intravenous methylprednisolone infusion. Blood will be collected for immune function (cytokines) testing at baseline, and months 3, 6, 9 and 12. MRI will be done at baseline as well as months 6 and 12 following initiation of treatment; if the disability measurements are stable or improved at any point in time, then ECP will be continued per protocol..

Patients in the ECP arm should have all of their treatments with the CELLEX[®] System. Patients randomized to the ECP arm must receive their treatment within 5 days of baseline visit.

In the ECP process, UVADEX[®] (methoxsalen) Sterile Solution will be injected directly the recirculation bag of the extracorporeal circuit after completion of the buffy coat collection. The dose of UVADEX[®] (methoxsalen) Sterile Solution will be calculated based on the standard treatment volume formula (See Section 6.2).

For the schedule of assessments, please refer to Section 0.

Figure 1: Study Design

ECP=Extracorporeal Photopheresis MRI: Magnetic Resonance Imaging

¹ Frequency of ECP treatments:

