6. TREATMENT

6.1 Control Arm: Corticosteroid Treatment

Patients randomized to the control arm will receive corticosteroids in Pulses of 1 gram of intravenous methylprednisolone every 4 Weeks for 52 Weeks.

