6.2 Study Arm: Extracorporeal Photopheresis

ECP will administered according to the following schedule:

Study Arm: Weeks 1-8: 3 times per week

Weeks 9-16: Twice per week

Weeks 17-36: Treatment on two consecutive days every 2 weeks (or optionally, one treatment per week)

Weeks 37-43: Once every 2 weeks

Weeks 44-52: Once every 4 Weeks

The CELLEX[®] System are integrated photopheresis systems that are approved in US and Europe, and marked specifically to perform photopheresis. With the CELLEX[®] System, whole blood is drawn from the patient, centrifuged and separated into its components: plasma, white blood cells, and red blood cells. The white blood cells and a portion of the plasma are collected in a separate chamber for treatment. The remaining plasma and red blood cells are returned to the patient untreated. This collection process is repeated over several cycles. The buffy coat suspension of white blood cells is then exposed to a predetermined amount of UVA light (photo activation) after being inoculated with UVADEX[®] (methoxsalen) Sterile Solution. Following the photo activation of the buffy coat suspension, the treated cells are returned to the patient.

Every attempt should be made to process 1500-2000 mL of blood during each treatment.

UVADEX[®] (methoxsalen) Sterile Solution is supplied in a 10 mL single-use vial. Each mL of solution contains 20 mcg of UVADEX[®] (methoxsalen) Sterile Solution. Each vial contains 10 mL of UVADEX[®] (methoxsalen) Sterile Solution, which is more drug than necessary for most treatments. However, the vials are designed for a single use. Therefore, there will be surplus of drug remaining in the vial at the conclusion of each treatment. Study center staff should NOT attempt to reuse any portion of this unused study drug once the seal has been compromised. The remaining UVADEX[®] (methoxsalen) Sterile Solution should be discarded after verification of dose by the study monitor as per study reference manual.

In the ECP process, UVADEX[®] (methoxsalen) Sterile Solution will be injected directly into the Recirculation Bag of the extracorporeal circuit after completion of the buffy coat collection, just prior to initiating photo activation. The dose of UVADEX[®] (methoxsalen) Sterile Solution used to inoculate these cells will be calculated based on the treatment volume collected during the plasma/buffy coat collection process, using the following formula:

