10.2.2 Analysis of Secondary Endpoints

The secondary endpoints include:

- Change in Plasma levels of Immunological Factors and Frequencies of IFN γ and IL-17 MBP-specific PBMC at months 3, 6, 9 and 12 compared with baseline
- MSFC 3 dimensional composite z-score at every 3 month time point through 2 years compared to baseline
- Expanded Disability Status Scale (EDSS) score at every 3 month time point through 2 years compared to baseline
- Percentage of subjects with improvement (as defined for the primary endpoint) at months 3, 6, 9 and 12 compared to baseline
- Occurrence of clinical relapse at any point in the study

- Interval change in T2 lesion number and volume on MRI scans obtained at months 6 and 12 compared to baseline
- The number and volume of gadolinium enhancing lesions on MRI scans obtained at months 6 and 12 compared to baseline
- Interval change in the number and volume of gadolinium enhancing lesions on MRI scans obtained at months 6 and 12 compared to baseline.
- Toxicity and Adverse events in both arms

For continuous outcomes, two-sample t-tests or Wilcoxon rank sum tests will be used to compare the treatment arms. For categorical outcomes, Chi-square tests or Fisher's exact test will be used to compare the treatment arms. The proportion of subjects who experience adverse events and serious adverse events will be summarized by treatment group descriptively; no inferential tests will be performed.

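### AE recording is prescribed at every ECP session, but no matching instruction covers the steroid infusions, so by-arm AE proportions are open to unequal capture of mild, transient events

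*Combined protocol and SAP*

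**What the plan says.** **General rules, both arms.** Section 8.2.2.1 makes the investigator responsible for collecting all AEs, "derived by spontaneous, unsolicited reports of patients, by observation and by interval open questioning". Section 8.2.2.4 requires that all AEs, "regardless of the relationship to study drug, will be recorded in the CRF". Section 8.2.6 provides for an interim history at each visit. Table 2 (section 9.1) lists AEs at screening, at baseline and at months 3, 6, 9 and 12 in both arms.

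**Additional rule, ECP only.** Section 8.2.2.4 continues: "In addition, the technician performing the ECP procedure will observe and record any AEs that occur during the procedure". Neither section 6.1, which sets the control treatment as "intravenous methylprednisolone every 4 Weeks for 52 Weeks", nor the visit descriptions in section 9.2 contain a comparable duty at an infusion.

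**Timing of control assessments.** Section 3.1 states: "Subjects in the control arm will be evaluated by MSFC and EDSS during the week prior to their next intravenous methylprednisolone infusion". This concerns MSFC and EDSS. It does not mention AEs.

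**Analysis.** Section 10.2.2 states: "The proportion of subjects who experience adverse events and serious adverse events will be summarized by treatment group descriptively". It rules out inferential tests on these proportions.

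**The concern.** Comparing the tolerability and safety of ECP with that of corticosteroids is a stated secondary objective (section 2.2), and AEs in both arms are a secondary endpoint (section 3.2.2). Part of the case for ECP is its favourable safety profile (sections 1.2 and 3.3).

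If the plan is followed as written, a mild event during an ECP session has a named observer with a recording duty. A similar event during a methylprednisolone infusion depends on the general rules: someone notices it and passes it on, the patient reports it unprompted, or the patient recalls it at a quarterly visit. Treatment is open-label, so blinding does not even out recording behaviour. With no tests planned and about 33 patients per arm, the displayed percentages are the safety evidence that a reader will use. An ascertainment difference could be read as a difference in harm.

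**Working it through.** The plan states no number of AE contacts and no expected AE rate, so there is no figure of its own to reproduce. The counts below come from its schedules.

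**1. ECP sessions (section 6.2)**
- "Weeks 1-8: 3 times per week": 8 × 3 = 24
- "Weeks 9-16: Twice per week": 8 × 2 = 16
- Weeks 17–36: 10 × 2 = 20, or 20 × 1 = 20 under the weekly option
- Weeks 37–43, every 2 weeks: 4 (weeks 37, 39, 41, 43), or 3 if rounded down
- Weeks 44–52, every 4 weeks: 3 (weeks 44, 48, 52), or 2 if rounded down

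Total: 24 + 16 + 20 + 4 + 3 = 67, or 65 with both part-blocks rounded down. The Synopsis splits the last two blocks at weeks 37–44 and 45–52, giving 24 + 16 + 20 + 4 + 2 = 66. The two schedules must be reconciled, but the choice does not affect this point.

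**2. Infusions (section 6.1).** 52 / 4 = 13.

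**3. AE capture routes named in the text, after baseline**

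| Route | ECP | Methylprednisolone |
|---|---|---|
| Spontaneous report, observation, open questioning | yes | yes |
| Scheduled AE visits (months 3, 6, 9, 12) | 4 | 4 |
| Named recorder during treatment | 65–67 sessions | none named for the 13 infusions |

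**4. Capture and exposure separated (illustration; q and c are assumptions).** Let q be the chance of a mild event at any one treatment, equal in both arms. Let c be the share of infusion-time events that is recorded, with full recording at ECP. The proportion with at least one recorded event is 1 − (1 − q)^67 for ECP and 1 − (1 − qc)^13 for controls.

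| q | ECP | Control, c = 1 | Control, c = 0.5 | Lost to capture | Due to exposure alone |
|---|---|---|---|---|---|
| 1% | 49.0% | 12.2% | 6.3% | 5.9 points | 36.8 points |
| 2% | 74.2% | 23.1% | 12.2% | 10.9 points | 51.1 points |
| 5% | 96.8% | 48.7% | 28.0% | 20.7 points | 48.1 points |

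The fifth column (c = 1 minus c = 0.5) is the ascertainment problem. The last column (ECP minus c = 1) is genuine treatment burden from 67 sessions against 13, and is not bias.

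**5. Dilution by other AEs (illustration).** Section 10.2.2 counts patients with any AE, not only treatment-time AEs. Suppose 50% of each arm truly has at least one treatment-time event. With λ = −ln(1 − 0.5), the control arm shows 1 − exp(−λc). Suppose also that a proportion B has some other captured AE, independently. The gap then shrinks by the factor 1 − B.

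| c | Control shows | Gap, B = 0 | Gap, B = 70% | Gap, B = 90% |
|---|---|---|---|---|
| 4/13 | 19.2% | 30.8 points | 9.2 | 3.1 |
| 0.5 | 29.3% | 20.7 points | 6.2 | 2.1 |
| 0.75 | 40.5% | 9.5 points | 2.9 | 1.0 |

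One patient in an arm of 33 is 1/33 = 3.0 points. The c = 4/13 row supposes that only the infusion immediately before each of the four scheduled visits is ever asked about.

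**The case against.** The best defence is that the protocol is silent about infusions; it does not exclude them. The general rules cover both arms and include collection by observation, and causality is assessed for corticosteroids as well as ECP (section 8.2.2.3.3). A Study Reference Manual, which is not among the documents, may contain instructions for infusion staff. This defence stands against three stronger readings that a reader might infer.

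- *AEs are not recorded at infusions.* No section says so. Only the written instruction is missing.
- *Nine of 13 infusions escape enquiry, leaving a false excess of about 31 points.* Questioning about the interval reaches back over all infusions since the last visit, and spontaneous reports remain possible. The 31 points also require that no patient has any other AE. In addition, equal per-patient risk over 67 sessions and 13 infusions implies a per-infusion event rate about 67/13 ≈ 5 times the per-session rate.
- *Controls are asked about AEs only three to four weeks after an infusion.* Section 3.1 fixes the timing of MSFC and EDSS. That AE enquiry shares this timing is an inference from Table 2.

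The consequences are also limited. SAEs must be reported within 24 hours in both arms (section 8.2.2.5), and many effects listed in Appendix 3 are not confined to infusion time.

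What the defence does not remove is the opening of the 8.2.2.4 sentence. It presents the technician's duty as additional to the general rules, and that addition is given to one arm only.

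**Conclusion.** The asymmetry is real and follows directly from the text: a prescribed recorder at about 65 to 67 ECP sessions, and no matching instruction for 13 infusions. The by-arm AE proportions are therefore open to differential ascertainment of mild, transient treatment-time events, probably under-recording them in the steroid arm. That direction assumes that a named observer records more such events than the general rules alone.

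The size cannot be computed. Under the assumptions shown, the effect on the any-AE proportion ranges from about 1 to 9 points when 70% to 90% of patients have another captured AE. It is larger if few do, and zero if infusion events are recorded as fully as ECP events. A reader might conclude that an excess of AEs with ECP would be an artefact, but the documents do not support that: events seen at a session are genuine ECP events, and more sessions mean more real exposure. Only descriptive tables are exposed; SAEs and the primary endpoint are largely unaffected. Severity: minor to moderate.

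**What to change.** 1. **Section 8.2.2.4.** Replace the technician sentence with one covering both treatments, for example: *Whoever gives an ECP session or a methylprednisolone infusion will watch for AEs during that treatment and enter them on a form common to both arms.* Do not add an open question about AEs since the last contact at each treatment. That would create about 67 enquiries about all AEs with ECP against 13 with steroids, a new imbalance, and about 67 × 33 = 2,211 enquiries in the ECP arm.

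2. **Section 10.2.2.** Keep the all-AE and SAE proportions by arm as planned. Add a supplementary table separating AEs recorded during treatment, also expressed per session or per infusion, from AEs collected at the common visits (months 3, 6, 9 and 12). Note beneath it that treatment contacts differ, about 67 against 13. The main table should not be restricted to common-visit events, because that would drop genuine ECP procedure events and spontaneous reports.

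**Cost.** About 13 × 33 = 429 short control-arm forms, completed by staff already giving the infusions, and one extra table. No new visits, and no change to treatment. It should be done prospectively, since unrecorded infusion events cannot be reliably recovered later.

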8.2.2.5 Reporting Serious Adverse Events

All SAEs, regardless of relationship to the study agent(s) or study procedure(s), must be reported to the investigator, or his designee, within 24 hours of observation or notification of the event. Instructions for reporting an SAE are provided in this section. The name(s) and contact details of the individual(s) who should be contacted regarding safety issues or questions regarding the study are also included in the Box on page 39 and in the Study Reference Manual.

The Investigator will review each SAE report and the investigator will evaluate the seriousness and the causal relationship of the event to study treatment. In addition, the Investigator will evaluate the expectedness according to the reference document (Investigator Brochure, Device

Instructions for Use (IFC) and the informed consent document). Based on the Investigator's assessment of the event, a decision will be made concerning the need for further action.

Hospitalization due to MS progression will be considered as an SAE. Hospitalization for an elective or planned procedure to treat a preexisting condition will not be considered as an SAE unless it results in one of the other outcomes listed above. Hospitalizations for study agent administration only will not be considered as SAEs. Details for the reporting of suspected unexpected serious adverse reactions (SUSARs) can be found in Section 8.2.2.7.

All SAEs will be recorded from signing of informed consent until the end of the study (Week 52).

Safety contact for study:

Safety Line Number: [contact]

Safety Fax Line:

Email: [name] <[contact]>

Investigator Responsible for SAE reporting: [name]

SAE reporting Instructions:

- Fax the SAE form and any supporting documentation to the Investigator.
- Telephone the Investigator to confirm that you have faxed a SAE form
- Provide investigator's name, your name, the telephone number where you can be reached, and the protocol number and title.

The minimum information required for an initial report is:

- Sender of report (name, address of investigator).
- Patient identification (screening/randomization number, initials, NOT patient name).
- Protocol number.
- Description of SAE.
- Causality assessment.

After receipt of the initial report, the Investigator will review the information and, if necessary, contact the involved physician to obtain further information for assessment of the event. The Investigator or his designee will be responsible for all information processing and reporting according to legal requirements following ICH E6 guidelines. The Sponsor-Investigator will be responsible for all safety reporting to the FDA. Details for the reporting of SUSARs and UADE's can be found in Section 8.2.2.7

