9.2.7 Week 52 through the End of Study

- From Weeks 44-52, patients will receive one ECP treatment every 4 weeks
- Patients admitted to the corticosteroid arm will receive a treatment once every month
- Before ECP on each day of treatment blood samples will be collected for the tests outlined on Table 1
- The following will also be performed at this time point:
 - Interim history, vital signs, physical exam.
 - Blood for immune parameters (sent to the UM Neuroimmunology Research Laboratory)
 - MSFC(every 3 months through 2 years)
 - EDSS (every 3 months through 2 years)
 - Adverse Events
 - Concomitant Medications
 - MRI with Gadolinium

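### Three safety sections give conflicting end dates for recording the same adverse events, and following the SAE section as written can drop late serious events judged unrelated

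*Combined protocol and SAP*

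**What the plan says.** Three sections of the protocol set an end date for safety recording.

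- **8.2.2.2 Definitions:** "AEs will be captured after informed consent signed until 30 days post the completion of the last intervention". A bracketed Week 52 follows that sentence.
- **8.2.2.4 Recording Adverse Events** names two possible ends: "Adverse event reporting will extend from signing of informed consent until completion of study (Week 52) or 30 days after the last study intervention". Nothing says which of the two dates applies.
- **8.2.2.5 Reporting Serious Adverse Events:** "All SAEs will be recorded from signing of informed consent until the end of the study (Week 52".

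The first two rules are not confined to milder events. Section 8.2.2.1 tells the investigator to "collect all AEs (both serious and non-serious", and Section 8.2.2.4 requires each AE report to state "whether the event is classified as serious".

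For events after the end of the study, Section 8.2.2.4 says that they "should be reported to the Sponsor by the investigator if the investigator considers there is a causal relationship with the study treatment".

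On treatment, Section 9.2.7 says: "From Weeks 44-52, patients will receive one ECP treatment every 4 weeks". Section 6.1 gives methylprednisolone at the same four-week interval over 52 weeks.

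**The concern.** Section 8.2.2.5 is the section staff will turn to for a serious event. It holds the 24-hour reporting duty, the form and the safety contact. Read as written, recording under it stops at Week 52, which may be the week of the last treatment.

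The provision for later events in Section 8.2.2.4 does not fully make up for this. Up to Week 52, Section 8.2.2.5 requires SAEs to be reported whatever their relationship to treatment. After the end of the study, reporting depends on the investigator's view of causality. The trial is open-label, so that view is formed with knowledge of the arm. The protocol also has a Sponsor-Investigator, so reporting to the sponsor adds little independent scrutiny.

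Three uses of the data are affected. Safety and tolerability by arm is a secondary objective (Section 2.2). Section 10.2.2 summarises the proportion of subjects with SAEs by treatment group. The data and safety monitoring board reviews all SAEs unblinded, but sees only the most frequent AEs, as blinded aggregates (Section 8.2.2.6). A late SAE that is never recorded as one is missing from all three.

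**Working it through.** The plan gives no figure to reproduce here. The check compares the stated end dates and counts days.

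**1. Which events does each rule cover?** Sections 8.2.2.1 and 8.2.2.4 together make SAEs a subset of AEs. A serious event 20 days after a last treatment in Week 52 is therefore:

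- inside the window of Section 8.2.2.2;
- inside or outside that of Section 8.2.2.4, depending on how *or* is read;
- outside that of Section 8.2.2.5.

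**2. How long is the uncovered period?** Assume that day 1 is the first day of Week 1. Week *w* then covers days 7(*w* − 1) + 1 to 7*w*, and Week 52 closes on day 364. For a last treatment on day *d*, the time inside the 30-day rule but outside the SAE sentence is

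(*d* + 30) − 364 = *d* − 334 days.

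| Last treatment in | Day *d* | 30-day window closes | Days beyond Week 52 |
|---|---|---|---|
| Week 44 | 302–308 | 332–338 | −32 to −26 |
| Week 48 | 330–336 | 360–366 | −4 to +2 |
| Week 49 | 337–343 | 367–373 | 3 to 9 |
| Week 52 | 358–364 | 388–394 | 24 to 30 |

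A negative value means that the Week 52 limit falls later than 30 days after treatment, so the SAE sentence gives the longer window.

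**3. Which row applies?** The documents do not say. Infusions every four weeks from Week 1 would end in Week 1 + 4 × 12 = 49. ECP every four weeks from Week 44 would end in Week 44 + 4 × 2 = 52. The Synopsis starts that last ECP phase in Week 45 instead, which would give Weeks 45 and 49.

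Under the first two of these illustrative schedules, the SAE sentence leaves 364 − *d* days of recording after treatment: 0–6 days for ECP (*d* = 358–364) and 21–27 days for control (*d* = 337–343). The gap could therefore differ by arm, but this is an illustration and not something the protocol fixes.

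**4. Size over the trial, if all 66 patients had the same last week:**

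- Week 52: 66 × 24 / 365.25 = 4.3 to 66 × 30 / 365.25 = 5.4 patient-years.
- Week 49: 66 × 3 / 365.25 = 0.5 to 66 × 9 / 365.25 = 1.6 patient-years.
- Week 48 or earlier: essentially none.

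**5. Does the visit schedule close the gap?** Table 2 marks AEs at 12 months but not in the column for the three-monthly visits through 2 years. Section 9.1 lets the 12-month visit fall a month either side of Week 52, so the last marked AE assessment can come before the last treatment. *End of study* is also used in two senses: Week 52 in Sections 8.2.2.4 and 8.2.2.5, and 2 years in the Table 2 column heading.

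**The case against.** A reader might infer that the plan follows non-serious events for longer than serious ones. The documents do not support that. No section limits the 30-day rule to non-serious events, so the fault is a contradiction about the same events. Nor is the SAE window always the shorter: for patients who stop treatment before about Week 48 it is the longer one.

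A reader might also infer that all serious events after Week 52 would be lost. That too goes beyond the text. Section 8.2.2.4 keeps related late events reportable, and the expedited-reporting duties in Section 8.2.2.7 carry no Week 52 limit. Timing after treatment is one of the causality criteria in Section 8.2.2.3.3, so an event soon after a session is not readily set aside. If staff follow Section 8.2.2.2, unrelated late SAEs are captured as well.

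Finally, 5.4 patient-years should not be read as an estimate. It needs every patient to be treated on the last day of Week 52.

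These objections stand, and they narrow the point. What remains is that the three sections cannot all be followed. A site that follows the section written for SAEs would be within the protocol in not recording late SAEs it judges unrelated.

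**Conclusion.** The inconsistency is real and should be corrected. The events at risk are SAEs judged unrelated that occur after Week 52 but within 30 days of the last treatment, and only if Section 8.2.2.5 is taken to override Section 8.2.2.2. The exposure per patient runs from about none to 30 days, depending on a last treatment date that the documents leave open; the trial-wide figure above is a ceiling. The day counts rest on Week 52 closing on day 364.

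For early stoppers the problem is different: the *or* in Section 8.2.2.4 leaves their end date undefined. No efficacy result depends on this point. It bears on how complete and comparable the SAE summary by arm is.

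**What to change.** Reconcile Sections 8.2.2.2, 8.2.2.4 and 8.2.2.5 into one window for all AEs, serious and non-serious: from consent to the later of the Week 52 visit and 30 days after the last ECP or methylprednisolone treatment, regardless of causality. The *later of* wording removes the open *or* and covers both late-treated patients and early stoppers. State also which date counts as the Week 52 visit when those assessments are brought forward at early termination (Section 9.2.8).

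The cost is wording in three sections and about one safety contact per patient. Treatment does not change.
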